RT have commissioned a number of evaluations of its programme within different hospital sites. A non-peer reviewed published evaluation undertaken on the programme in St Mary's hospital in London by NPC associates^{18,26} showed promising findings, regarding reducing hospital re-attendance rates for violence (a statistically significant fall compared to a pre-programme control group). YP using the service and professionals referring into it were supportive of the programme. However, there were limitations in the study design which affected the ability to draw a causal conclusion. Similarly, an evaluation of the programme in the Queen's Medical Centre undertaken by research staff there²⁷ showed lower re-attendance rates for YP who participated in the programme (both short term crisis support and full programme of work), compared to those YP who were eligible for the programme but did not engage with it. These results were found for re-attendance for any reason and specifically for violence or assault.

Mechanism for action and key outcomes

During the co-design phase we worked with RT and their partners (Dartington Service Design Lab) to undertake a Theory of Change exercise. This work involved key stakeholders and is on-going but a draft has been produced and is described below. The work has helped clarify what the different components of the programme are and the likely channels which have outcomes for CYP. In turn, this has enabled us to clarify the short-, medium- and long-term outcomes that are expected. As a result, during our sessions, we have considered the outcomes at length in consultation with YEF and RT both separately and as part of a co-design phase. Following the co-design stage, it became clear that the primary outcome should be reattendance coded for a violence or abuse related reason to hospital within 12 months from their initial discharge date. These data are available for both intervention and controls (see detail later) and we are confident that there will be sufficient power to distinguish the two groups. The secondary outcome will be mortality by any cause one year post contact with RT (this will draw on NHS data captured in the Summary Hospital level Mortality Indicator and other data which captures mortality beyond 30 days post discharge).

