 - c. Redthread are able to retain CYP in support within the intervention to work through the action plan. At least 60% of planned numbers within the pilot period should be retained for a sufficient

period to complete this work. Anything below that is cause for concern (Yellow) with a need to pause (Red) if the response is below 40%.

3. Measurement
 - a. Hospital admission records (primary outcome)
 - b. Mortality data (secondary outcome)

Follow up data collection will continue for 1 year after the intervention.

It will be important to see how easily data can be matched between NHS and RT records. Not being able to match at least 80% of referrals is cause for concern and needs to be discussed (Amber), anything below a 60% match is serious cause for concern (Red) and may require us to revisit this method of capturing data.

Some key data issues such as incomplete/missing data or noncompliance or higher attrition rates than expected need to be considered. A certain level of missing data can be handled using statistical techniques, but quarterly audits should prevent this from becoming a serious problem.

These ratings relate to the feasibility of the methods of data collection of the pilot. Failure to meet success criteria, does not necessarily mean that the main evaluation should be abandoned, but will suggest that the proposed design or methods require revision. Provided the above are met or feasible alternatives can be found, we will recommend that we proceed to an efficacy trial, which will be completed via a separate ethics application. YEF will then reflect on the evidence the evaluation provides before a decision is made about the transition to the efficacy study.

The progression criteria will remain under review with more specific suggestions made as the evaluation proceeds (e.g. when it is clearer what a realistic proportion of completions of the SDQ might be possible with this cohort). Following the successful completion of this first year then we will focus on developing success criteria for the two-year efficacy study.

Methods

Study design

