1. RT staff - Staff will be interviewed at the start of the intervention and throughout as part of the process evaluation. Participants will be those working directly on the project (programme managers and a representative of each job role across the four hospital sites). The size of these teams vary by hospital site, we will use a mix of one-to-one interviews and focus groups to ensure we speak with as many members of these teams as possible. This part of the pilot has been reviewed and approved by UoB ethics.
2. NHS clinicians and other staff who refer CYP to the RT teams – We will aim to interview (perhaps in a focus group) around 4-6 individuals in each of the 4 hospital sites. We will ask RT to identify appropriate staff members, provide them with the Adult Participation Information Sheet and gain consent for their contact details to be passed to the study team. Researchers will gain written consent prior to commencing the interview.

3. Community partners –non-hospital personnel who work with Redthread in joint case work, and representatives of organisations receiving onward referrals. We will aim to interview (perhaps in a focus group) around 4-6 individuals in each of the 4 hospital sites. We will ask RT to identify appropriate staff members, provide them with the Adult Participation Information Sheet and gain consent for their contact details to be passed to the study team. Researchers will gain written consent prior to commencing the interview.
4. CYP who are engaged in the intervention. We will aim to interview 10-20 CYP and gather quantitative data from all those taking part in the intervention. The CYP eligible for the intervention are those who have attended one of 4 hospital ED as a result of violence or deemed at risk of exploitation or abuse by a referring clinical member of staff. CYP can also be referred should they present in a different part or department of the hospital or if information about their risk factors transpire following their admission (see eligibility criteria for RT in the theory of change (page 1- introduction for more detail).

For the impact evaluation, the participants will consist of:

1. Intervention group: CYP (aged 10-17) who have undergone the intervention in any of the four sites (see eligibility criteria).

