to reflect upon it. CYP will be interviewed by experienced University researchers either face to face in local RT offices, or online depending on their preference. All the involved UoB staff are experienced in trauma informed interviewing and working with children. We will seek a maximum variation sample¹⁹ to give us a range of different backgrounds, experiences, referral routes and ethnic backgrounds. We will ask youth workers to refer to us **all** CYP they consider able to consent and communicate in English language to be invited for interview. This will avoid youth workers only referring those young people where they think they've had more success and who are likely to give positive responses. We will ask RT staff to provide CYP and parents/carers with Participant Information sheets (audio and translated version will also be made available) during their initial meeting in hospital. They will be consented into the study during their post-discharge meeting with RT. Researchers will ask the CYP to sign an additional consent statement prior to participating in an interview. It is likely that where consent is needed from parents/guardians for those under 16, this will be obtained via phone or email and recorded appropriately on the consent form. Thank you tokens in the form of shopping vouchers (£20) will be offered to CYP participating. We will ask RT to systematically gather information on those CYP who refuse an interview so we can assess differences between those who agree to and refuse an interview. We will ask RT staff to provide CYP and parents/carers with Participant Information sheets (audio version will also be made available) during their initial meeting in hospital. They will be consented into the study during their post-discharge meeting with RT.

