As highlighted above, we aim to undertake a QED with PSM to ascertain impact. The PSM study will consist of collecting data from the treatment group (from the four RT hospitals) and then, with the support of the relevant health informatics teams at the sites, identify a suitable group of controls who have not used the service from at least one of the existing sites (but who have not refused that service as including those who refuse service would create a selection bias). This could be drawn from contemporaneous or historical data, depending on the processes RT uses to gather referrals; for example, whether there would be a group of suitable CYP not approached by RT. This data will be provided to us without any personal identifying information. The groups will then be propensity score matched to identify the most suitably similar controls based on a variety of demographic and clinical data that we have in both the hospital record and RT dataset. This is likely to include age, gender, severity and nature of their injury, or level of risk to the CYP based on RT's eligibility criteria (weapon-related injury or a serious assault with the intention to do serious harm; concerns that incidents or individuals may be gang affiliated or have been exposed to or experienced violence/abuse; concerns that an individual is at risk of further harm or abuse; concerns or disclosures of domestic abuse, sexual violence, including historic sexual violence/abuse; concerns of (Child) Sexual Exploitation or (Child) criminal exploitation). These variables are chosen because they are related to both the treatment and the outcome and are common in the literature (see e.g. Shibru et al., 2007).

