With regard to registration, we intend to publish this protocol in BMJ Open.

All correspondence with the REC will be retained.

It is the Chief Investigator's responsibility to produce the annual reports as required.

The Chief Investigator will notify the REC and sponsor of the end of the study.

An annual progress report (APR) will be submitted to the REC and sponsor within 30 days of the anniversary date on which the favourable opinion was given, and annually until the study is declared ended.

If the study is ended prematurely, the Chief Investigator will notify the REC and sponsor, including the reasons for the premature termination.

Within one year after the end of the study, the Chief Investigator will submit a final report with the results, including any publications/abstracts, to the REC and sponsor.

Indemnity

The University has in force a Public Liability Policy and/or Clinical Trials policy which provides cover for claims for "negligent harm" and the activities here are included within that coverage.

Data protection

The six lawful bases for processing are set out in Article 6 of the UK GDPR (one of which must apply when data is processed). A relevant basis for processing personal data here is the 'public task' basis.

For qualitative data, the most relevant principle/basis is **consent**; the individual has given clear consent for you to process their personal data for a specific purpose. Informed Consent will be obtained – this is where participants receive information outlining the nature of the research, what they are being asked to do, their

right to refuse to take part without negative consequences and their right to withdraw from the research during the fieldwork and up to two weeks after they finish working with RT.

Regarding **confidentiality**, participants will be informed prior to and post the interview process that the information they provide will be kept strictly confidential and that no identifying information will be available to anyone external to the research team. Confidentiality will be preserved (for quantitative and qualitative data) through steps such as (1) assignment of participant numbers/pseudonyms, (2) deletion of audio files post-transcription, (3) transcripts / consent forms stored in a locked cabinet at the University, and (4) electronic data held on password protected spaces only accessible to researchers.

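### The primary outcome counts from discharge, but treated-group membership depends on later steps that controls do not face, so early losses can leave the treated group and may enter the controls

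*Protocol*

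**What the plan says.** **Time zero.** Under Mechanism for action and key outcomes, the primary outcome is "reattendance coded for a violence or abuse related reason to hospital within 12 months from their initial discharge date". Success criteria and/or targets describes the window differently: "Follow up data collection will continue for 1 year after the intervention". Mortality is counted for one year from contact with RT, a date that an uncontacted or historic control does not have.

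**Entry to the treated group.** Participants and the Inclusion/exclusion criteria define the intervention group as CYP aged 10 to 17 who have gone through the programme at one of the four sites. In the bullet on CYP interviews under Process/implementation activities, information sheets are given in hospital, and then: "They will be consented into the study during their post-discharge meeting with RT". The same bullet adds: "Researchers will ask the CYP to sign an additional consent statement prior to participating in an interview".

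**Entry to the control group.** Controls are eligible CYP who did not take part, including referred CYP whom RT could not contact, or historic cases. Those who refused RT are excluded. Under Control group data collection: "This data will be provided to us without any personal identifying information". No consent step is described for them.

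**Coverage and withdrawal.** Participants says the team will "gather quantitative data from all those taking part in the intervention". Data protection names public task as a basis for personal data. Its paragraph on qualitative data then gives a "right to withdraw from the research during the fieldwork and up to two weeks after they finish working with RT".

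**The concern.** For controls, eligibility and the outcome clock both start at the index hospital episode. For treated CYP the clock also starts at discharge, but membership is settled later, by taking part in the programme and, on the natural reading, by consenting at a meeting after discharge. What happens in between can decide who is in the treated group.

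A CYP who dies before the meeting cannot be in it. A CYP who is lost to RT, or who reattends and is never engaged, may not be in it either. If RT never reached that CYP after referral, the definition allows the same person, with the same event, to be used as a control.

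All of these routes lower the treated event rate relative to controls. The planned propensity score uses baseline characteristics and cannot correct for membership decided after time zero. The Rosenbaum bounds planned under Impact data analysis address unmeasured confounders, not mismatched starting points. A later analysis plan cannot restore CYP who never entered the dataset, so this has to be settled at the protocol and REC stage.

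**Working it through.** **1. Does the consent sentence reach the impact evaluation?** It stands in the interview bullet, which argues for a narrow reading. But interview consent is described as additional, so the consent at the post-discharge meeting must cover something wider. Data collection information also lists identifiers, reattendance and mortality together for treated CYP. The wider reading is therefore the natural one, though no sentence expressly limits the impact dataset to consenters. The time-zero problem does not rest on this sentence alone, because having gone through the programme is also known only after discharge.

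**2. The protocol's own figures.** It states no figure for early loss. Its planning figures reproduce:
- Per-group size for d = 0.2, 80% power, two-sided 5% (assumed, as alpha is not stated): 2 × (1.960 + 0.842)² / 0.2² ≈ 392.5, so 393 rounded up, against 392 stated.
- Expected control events: 392 × 0.078 = 30.6; variance 392 × 0.078 × 0.922 = 28.19, as stated.

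**3. Loss from the treated group only.** Inputs: p = 0.078 (the protocol's illustrative US rate), n = 392 per group, no true effect. Assumptions: the meeting takes place 2 or 4 weeks after discharge, events are spread evenly over the year, and every CYP with an event before the meeting is lost. Let f be the share of 12-month events before the meeting. The treated rate is p(1 − f)/(1 − pf).
- 2 weeks: f = 14/365 = 0.038; rate = 0.078 × 0.9616 / 0.9970 = 7.5%; RR 0.96; events lost 392 × 0.078 × 0.038 ≈ 1.2.
- 4 weeks: f = 28/365 = 0.077; rate = 0.078 × 0.9233 / 0.9940 = 7.2%; RR 0.93; events lost ≈ 2.3.

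**4. The same CYP also counted as controls.** This is possible only with contemporaneous controls. With m lost CYP, the control rate is (30.576 + m)/(392 + m).
- 2 weeks: (30.576 + 1.17)/(392 + 1.17) = 8.1%; RR = 7.52/8.08 = 0.93.
- 4 weeks: (30.576 + 2.35)/(392 + 2.35) = 8.3%; RR = 7.24/8.35 = 0.87.

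**5. Sensitivity.**
- If only half of the early-event CYP are lost, f halves. The treated-only RR is then 0.98 at 2 weeks and 0.96 at 4 weeks.
- If events run at twice the even rate in the first 4 weeks (f = 0.153), total loss gives RR 0.86, or 0.75 with crossing into controls.
- In standardised units, with SD √(0.078 × 0.922) = 0.268, the treated-only shift in step 3 is 0.01 to 0.02, against the planned 0.2.

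**The case against.** The strongest reply is that the protocol never says the hospital outcomes are limited to consenters. The consent sentence belongs to the qualitative work, and quantitative data are wanted from everyone taking part. The NHS–RT linkage criterion is set on referrals, and the Theory of Change has RT seeking consent for data storage and sharing when it approaches the CYP after referral. The pilot also disclaims causal inference under Sample size. The first points stand as far as they go: the consent gate is a reading, not an express rule. They do not remove the requirement to have gone through the programme. The disclaimer does not close the matter, because Success criteria and/or targets allows pilot data to contribute to the final analyses.

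A reader might infer more than the text supports, in five ways:
- *That treated CYP are event-free by construction until consent.* They are not. The window runs from discharge, so an early reattender who is later engaged and consented still counts. RT also reviews hospital systems and may meet that CYP again. Strict immortal time applies only to death.
- *That withdrawal removes hospital outcomes.* The withdrawal right is written in the paragraph on qualitative data. Its effect on linked records is not stated either way.
- *That stopping contact with RT loses the outcome.* It does not delete a hospital record, and treated reattendance is already listed as coming from NHS informatics or RT.
- *That selection acts on the treated side alone.* Refusers are excluded from the controls too.
- *That the bias is large, with risk ratios near 0.75.* That needs a longer delay, many early events or crossing into controls, together with total loss. The protocol gives no figure for any of these.

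**Conclusion.** The concern holds in limited form. Outcome time starts at discharge, treated-group membership is fixed later, and controls face no matching step. CYP who have an event or are lost before that step, and who never reach it, can leave the treated group and, with contemporaneous controls, may be counted there. The direction favours RT, and matching on baseline data does not correct it.

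The size is not established. For a 2 to 4 week delay at constant hazard, RR 0.96 to 0.93 (0.93 to 0.87 with crossing into controls) is an upper bound, because it assumes that every early-event CYP is lost. The true effect is probably smaller. A longer delay or front-loaded risk would enlarge it, and the protocol gives neither. At about one or two events per 392 this would not decide the result alone, but it is avoidable and would carry into any pooled efficacy analysis.

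**What to change.** For the impact evaluation:
- State that inclusion of treated CYP does not depend on the post-discharge study consent. Identify them from RT referral and acceptance at the index attendance.
- Take reattendance and mortality for both groups through the same pseudonymised informatics route and from the same discharge date, subject to NHS REC and HRA approval. Bring the other follow-up wordings into line with that date.
- Keep the post-discharge consent for interviews, SDQ/SRDS and the identifiable archive transfer.
- If consent or engagement must define the treated group, set a common landmark after discharge, start the clock there in both groups, and require both to be event-free to that point.
- State whether linked outcomes are kept after withdrawal, and report how many CYP and events are lost before consent.

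The cost is mainly protocol, information-sheet and REC wording, since hospital records are already the planned source. One small downside is that non-consenters' outcomes could not enter the named archive.

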- For CYP who don't have an effective support network who are facing extremely high levels of complex risk or harm, or require further support, RT offer a longer intervention, usually lasting up to three months, although this can be longer. A more comprehensive risk and needs assessment is completed by the youth worker in partnership with the CYP, and a joint action plan is agreed. Actions can include support navigating statutory systems, casework around healthy relationships or managing difficult emotions, support to (re-)engage with education, securing alternative accommodation, accessing mental health or substance misuse support, accessing financial support and welfare benefits, relational referrals to community or statutory partners and diversionary activities, supporting the CYP to advocate for themselves in multi-agency meetings, or goal-setting and aspirational exercises.

When closing a case, RT complete a comprehensive end assessment with each CYP, and follow up six months after case closure with the CYP and other key workers to review progress.

RT provide a dedicated, trained, highly skilled team in each hospital site made up of the following roles (The precise team combination varies per site):

- Programme Manager (oversees teams in each locality, covering multiple sites, safeguarding and partnerships lead);
- Team Leader (manages team, involved in partnership working and multi-agency work, carries a smaller caseload, delivers training to professionals);
- Senior Youth Intervention Practitioners (SYIP) (carries a caseload, delivers training to professionals, leads on projects);
- Youth Intervention Practitioner (YIP) (carries a caseload, delivers training to professionals);
- Programme Coordinator (data and administration lead);
- Counsellor (Birmingham only) (upskills practitioners, carries a small caseload of high risk young people);

- Young Women's Worker (some London sites only) (carries a caseload, specialist support for women, delivers training to professionals);
- Independent Domestic Violence Advocate/Advisor (seconded from Solace Women's Aid to 3 London sites, working in partnership with team to support YP affected by domestic violence).

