The matching is done by comparing the probability that an individual is assigned to the treatment group. Therefore, a matched pair comprises two individuals with the same probability of being assigned to the treatment group, yet one of them belongs to the control group. This probability is called the propensity score. The first step of PSM is to use logistic regression to calculate the propensity scores of each individual in the sample; the second step is to match these individuals according to their propensity scores. Once a propensity score has been calculated for each observation, we will ensure that there is overlap in the range of propensity scores across treatment and comparison groups by examining the scores graphically. A second check for the quality of matching is that, the propensity scores should have a similar distribution ("be balanced") in the treated and comparison groups. We will obtain an estimate of the propensity score's distribution by splitting the sample by quintiles of the propensity score. Because the number of individuals in the control group might be different than those in the treatment group, we will use kernel-based matching. We prefer the Epanechnikov kernel with a bandwidth of 0.06, which are common choices in the literature (see, e.g., Heckman, Ichimura and Todd, 1997).

We will ensure that there is a data sharing agreement between UoB and RT and UoB and the participating NHS trusts to support these activities.

Outcomes

For contextual information, following a co-design stage working with the intervention providers, it became clear that the primary outcome should be readmission (specifically violence/abuse related) to hospital at 12 months. These data are available for both intervention and controls and we are confident that there will be sufficient power to distinguish the two groups as well providing a comparable estimate with the published literature. The key secondary outcomes will be mortality by any cause one-year post contact with RT (this will draw on NHS data captured in the Summary Hospital level Mortality Indicator and other data which captures mortality beyond 30 days post discharge). We also plan to pilot the collection of the strengths and difficulty questionnaire (SDQ) and self-report delinquency scale (SRDS). However, the latter will be piloted in the opening phases of the study, as it is not likely we will be able to collect this data on control groups.

Control quantitative data

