We foresee challenges in the collection of hospital data from the intervention and control sites. However, we have experience in working with NHS trust site directors, health informatics teams, and emergency departments and believe that these challenges are ones that we can address. We have discussed with RT who will provide us with the treatment data and will support our team in the extraction of pseudo anonymised control data supported by the relevant health informatics teams who will assign case IDs to those in the control group.

We will use this phase to explore whether it will be possible to collect control data on current cases, who do not receive support from RT, or whether it will need to be constructed from historic data. Discussions of RT practice during the co-design phase highlighted that RT staff in hospital sites do review hospital admissions to check for missed referrals and that they follow up referrals made when staff are not on duty. This risks contaminating any concurrent control group and reduces the pool of eligible CYP for such a control group.

During this phase we will complete a Template for Intervention Description and Replication (TIDieR) Checklist for the proposed control sample as we have done during the co-design phase for the intervention. This will include defining precisely what Business as Usual (BAU) consists of across sites. Mostly likely, this will be statutory safeguarding practices, although it may well be that this varies from one Trust to another and this will, of course, influence the effect size found in the intervention. The implementation study will aim to track both the intervention and assess what the comparison group receives.

Sample size

During the co-design phase we identified approximately 300 CYP (aged under 18 years) are engaged in a longer term programme annually across all 13 ED sites. Our sampling considerations have been informed by existing literature on the topic.^{3,17} Much of the existing literature to date has focussed on criminal justice outcomes with no comparable study examining the risk of re-hospitalisation.

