Our research team for this project is reasonably diverse with regards to sex, age and ethnicity. We recognise that we will be speaking to different groups of participants who are also likely to be diverse with regard to their individual characteristics and that the interaction between the researcher and participant can affect the extent and quality of data gathering. The RT intervention is not suitable for the use of peer researchers as CYP do not tend to remain in contact with the service once they have finished their work. As such we will ensure that our researchers are mindful of diversity of the groups being interviewed, and in the case of the CYP, the sensitive nature of the topics covered. However, we will not be able to offer interviewees a choice of interviewer. The training of our staff will be key to our ability to safeguard and protect CYP participating in the study.

Data collection information

Participants	Data collected	Source	Details
CYP	
 Personal identifying information Demographic information Referral information Engagement with RT SDQ/SRDS responses Reattendance at hospital data Mortality data 	
 RT RT RT RT UoB online survey platform NHS informatics team/ RT Summary Hospital level Mortality Indicator 	(*All data on CYP will be passed to YEF at which point personal details will be replaced with a Pupil Matching Reference number from the Department for Education- pseudo anonymised).
NHS / RT / Community partner organisation staff	
 Contact details/ employer name and Job role 	
 Provided by staff leads after consent given 	For researchers to arrange interview- deleted after contact made and assigned ID to reflect employer / role group.
Controls	
 Demographic information Referral information Severity and nature of injury/ level of risk to the CYP based on RT's eligibility criteria. Reattendance at hospital data Mortality data 	
 NHS informatics team 	To support propensity score matching

Outputs

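### The primary outcome is return to hospital, but its only named sources are the sites' informatics teams plus Redthread for treated cases, so missed returns may differ by group in either direction

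*Protocol*

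**What the plan says.** - **Outcome.** Under 'Mechanism for action and key outcomes', the primary outcome is "reattendance coded for a violence or abuse related reason to hospital within 12 months from their initial discharge date". The 'Outcomes' section also refers to hospital in general, not to the index hospital or a participating Trust.
- **Sources.** In the 'Data collection information' table, the reattendance source is "NHS informatics team/ RT" for treated CYP and "NHS informatics team" for controls.
- **Reach.** 'Control group data collection' has controls identified "with the support of the relevant health informatics teams at the sites" and provides for a "data sharing agreement between UoB and RT and UoB and the participating NHS trusts". 'Control quantitative data' adds: "We have discussed with RT who will provide us with the treatment data". No national or cross-Trust attendance source is named. For mortality, by contrast, the protocol names an NHS indicator and further data reaching beyond 30 days after discharge.
- **Programme content.** Longer-term support can include "securing alternative accommodation, accessing mental health or substance misuse support" ('Intervention'). The Theory of Change also lists emergency accommodation under short-term crisis support.
- **RT contact.** RT follows treated CYP up six months after closing the case, with the CYP and other key workers.

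**The concern.** A violence-related return to a hospital outside the participating Trusts does not show up as missing data. It shows up as a CYP with no event. If the same share of returns were lost in both groups, the risk ratio would be unchanged and only the absolute difference would shrink. If the shares differ, the primary comparison is biased.

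Nothing planned would detect this:
- Propensity matching uses baseline characteristics.
- The Rosenbaum bounds in 'Impact data analysis' address unobserved covariates, not unrecorded outcomes.
- The measurement criterion (concern below 80% of referrals matched between NHS and RT records, serious concern below 60%) could be met in full while every return elsewhere stayed invisible.

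The table already gives the two groups different ascertainment, and the programme itself may affect where a treated CYP lives. Both are reasons to doubt that capture is equal.

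**Working it through.** **1. The plan's own sample size.** Inputs from 'Sample size': d = 0.2, power 80%, equal groups. The significance level is not stated there, so two-sided 5% is assumed. n = 2 × (1.96 + 0.8416)² / 0.2² = 392.4, rounded up to 393 per group. The stated 392 is reproduced, and power at 392 is 79.96%. No figure in the protocol is wrong on this point; the issue is how the outcome is captured.

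**2. Formula for the bias.** Let p be the true 12-month rate in both groups (no programme effect), and let u_T and u_C be the shares of treated and control returns that are missed. Observed rates are p(1 − u_T) and p(1 − u_C). The spurious risk ratio is (1 − u_T)/(1 − u_C), which does not depend on p.

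**3. Numbers.** p = 7.8%, the protocol's illustrative control rate from a US study; n = 392 per group. All values of u_T and u_C are assumptions. The last column is Φ(difference/SE − 1.96) for a simple unmatched comparison of two proportions; with equal capture it would be 2.5%.

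| Control missed | Treated missed | Observed control | Observed treated | Risk ratio | Fewer treated events | Chance of a significant apparent benefit |
|---|---|---|---|---|---|---|
| 10% | 15% | 7.02% | 6.63% | 0.94 | 1.5 | 4% |
| 10% | 20% | 7.02% | 6.24% | 0.89 | 3.1 | 6% |
| 10% | 30% | 7.02% | 5.46% | 0.78 | 6.1 | 15% |
| 10% | 40% | 7.02% | 4.68% | 0.67 | 9.2 | 29% |

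Second row in full: 7.8% × 0.90 = 7.02%; 7.8% × 0.80 = 6.24%; 0.80/0.90 = 0.89; 392 × (0.0702 − 0.0624) = 3.1 events.

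Reverse case, with 20% of control and 10% of treated returns missed: 0.90/0.80 = 1.125, or about 1.13, an apparent harm of 7.02% − 6.24% = 0.78 percentage points.

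**4. Evidence on the sign.**

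| Could lower capture in treated CYP | Could raise capture in treated CYP relative to controls |
|---|---|
| Help with alternative or emergency accommodation, which might take a CYP out of area | RT is a second reattendance source for treated CYP only |
| | RT is in contact again six months after case closure |
| | Controls may include referred CYP whom RT could not reach, who may themselves be mobile |

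The protocol gives no frequency for any of these.

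**The case against.** A reader might infer that the programme moves CYP away from the sites, so that returns go uncounted more often in the treated group and mimic a benefit. The protocol does not support that direction. Accommodation is one of many things support can include. No frequency is given, and new accommodation need not be outside the Trust's catchment. Care for controls is still to be defined; it is most likely statutory safeguarding, and nothing says that this never relocates a child. The table gives treated CYP the extra source, although the protocol does not say that RT follow-up records returns to other hospitals. A calculation that assumes 10% to 20% of treated CYP move, that all their returns are lost and that no control moves gives a 10% to 20% reduction only because that was put in. Major Trauma Centre status and ageing out of a children's hospital are not specific to one group, and age is a likely matching variable. These objections stand.

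Two more stand in part. First, the protocol never says that only participating Trusts' records count; this is inferred from the named sources and agreements. If a wider source is intended, the protocol should name it. Second, the pilot disclaims causal inference, the risk register allows for alternative data sources, and the efficacy stage will have its own protocol. That lowers the urgency. But pilot data may be carried into the final analysis, the pilot report will compare outcomes between groups, and testing data collection is one of the pilot's purposes.

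**Conclusion.** The concern holds as a gap in ascertainment whose sign is unknown. The endpoint is worded as return to hospital in general, the named sources appear to reach only participating Trusts and RT, and those sources differ by group. Returns elsewhere would then count as no event, and no planned analysis or progression criterion would reveal it. With no true effect, the spurious risk ratio is 0.89 if 20% of treated and 10% of control returns are missed, and 1.13 if those shares are swapped. An excess of 5 to 30 percentage points missed among treated CYP gives 0.94 to 0.67 when 10% of control returns are missed. These figures rest on assumed shares, and the 7.8% rate is itself only illustrative. They show sensitivity and do not estimate the bias. The plan should be changed before data are extracted; this does not invalidate the pilot.

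**What to change.** Amend the 'Data collection information' table and the data-agreement text under 'Control group data collection'.

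1. **Same ascertainment in both groups.** Take the primary outcome from the same NHS source, with the same search and the same 12-month window. Do not count returns known only from RT in the primary comparison. Where governance allows, have all participating Trusts searched for both groups before records are de-identified.
2. **Accurate name.** Call the endpoint *reattendance at a participating Trust* unless a source covering all hospitals is used. Plan such a source for the efficacy stage. A search of the participating Trusts makes ascertainment alike but will not find returns to other hospitals.
3. **Report and test.** Report known out-of-area moves by group. Pre-state a sensitivity analysis that varies the share of missed returns separately in each group, in both directions.

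Two other remedies may suggest themselves but should not be used. Restricting by home postcode at the index attendance does nothing about later moves. Assigning the control event rate to treated CYP who move would erase any true benefit of moving.

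**Cost.** Returns reported only by RT leave the primary count. A cross-Trust search adds governance work, and the protocol requires a formal amendment for changes to study procedures. The renaming and the sensitivity analysis need only added text and a short analysis; reporting moves depends on what the records hold.
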